13.3.3 Photopic Monocular DCIVA

Phase I/Pilot subjects will be excluded from the analysis of this endpoint.

Photopic monocular DCIVA (logMAR) at 66 cm in first eyes at Post-Operative Visit 4 (Day 120 to 180 after second eye IOL implantation) will be summarized and analyzed similarly to the second primary effectiveness endpoint in [Section 13.3.2](#) using a seed of 1340584231 for multiple imputation.

13.4 Secondary Effectiveness Analyses

13.4.1 Photopic Binocular DCNVA

Phase I/Pilot subjects will be excluded from the analysis of this endpoint.

Photopic binocular DCNVA (logMAR) at 40 cm at Post-Operative Visit 4 (Day 120 to 180 after second eye IOL implantation) will be analyzed using an ANCOVA with DCNVA as the dependent variable and treatment and site as fixed factors. The treatment effect (LS mean for Test group IOL minus LS mean for Control group IOL) will be estimated in addition to a two-sided 90% CI. The analysis will be based on observed data for ITT, mITT, and PP sets. Multiple imputation of missing data will not be applied.

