## **13.5 Statistical Analysis**

Summaries for continuous variables will include the sample size, mean, standard deviation, median, minimum, and maximum. Summaries for categorical variables will include the tabulation of frequencies and percentages.

All effectiveness analyses will be presented for the ITT Set in addition to the analysis Set(s) mentioned below.

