#### 13.5.3.2 Photopic Monocular DCNVA

Photopic monocular distance-corrected near visual acuity (DCNVA) at 40 cm in first eyes at Post-Operative Visit 4 will be summarized using continuous summary statistics in logMAR units by treatment assignment for the mITT Set Phase II and III subjects (combined). The DCNVA best distance data from the Phase I/Pilot subjects will be excluded from hypothesis testing and will be summarized separately from the data of the other subjects.

If there are missing mITT analysis set monocular DCNVA data at Visit 4, then missing data will be imputed using the Markov chain Monte Carlo (MCMC) multiple imputation method. After imputation of missing data, the statistical hypotheses will be tested using a statistical model with treatment and site as fixed factors by imputation.

An overall p-value resulting from the multiple imputation method will be estimated. The treatment effect (mean Test group IOL VA minus mean Control group IOL VA) in logMAR units will be summarized using continuous summary statistics and a two-sided 95% confidence interval. If the p-value from the multiple imputation analysis is less than or equal to 0.05 and the treatment effect is less than or equal to -0.20 (i.e., the Test lens mean logMAR VA is at least 0.20 less than the mean for the control), then it will be concluded that the Test IOL is statistically and clinically successful (i.e., superior to the Control IOL) in this outcome.

The previous continuous summary statistics will also be provided for the Per Protocol Set. However, superiority will not be evaluated with the PP Set and statistical success will not depend upon the results of the PP analysis.

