### **13.5.4 Secondary Effectiveness Analyses**

Photopic binocular DCNVA, UCNVA, DCIVA, and UCIVA at Post-Operative Visit 4 will be converted from letters correct to logMAR units and compared between treatments using the methods described above for DCNVA and DCIVA. The near and intermediate VA data from Phase I/Pilot subjects will be excluded from near and intermediate VA hypothesis testing and will be summarized separately from the near and intermediate VA data of the other subjects. The endpoints will be evaluated hierarchically in the following order: DCNVA, UCNVA, DCIVA, and UCIVA.

First eye BCDVA, DCNVA, and DCIVA (all in logMAR units) at Visit 5 will be summarized using descriptive statistics (mean, standard deviation, minimum, and maximum) for the ITT Set by treatment group (MX60EF Trifocal MIOL, MX60E IOL). The means at Visit 5 for each of these outcomes will be compared between the treatment groups qualitatively.

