## **13.6 Additional Statistical Considerations**

### **13.6.1 Handling of Missing Data**

Imputation of missing primary endpoint data is described in Section 13.5.3 above. Unless otherwise specified in the SAP, missing data will not be imputed.

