9.2 Dropouts or Missing Data Handling

For primary analysis of primary and secondary effectiveness endpoints, missing data will not be imputed for the non-inferiority analyses and will be imputed using multiple imputation Markov Chain Monte Carlo (MCMC) methods for the superiority analyses (see [Section 13.3.2](#)). For analyses of safety and exploratory effectiveness endpoints, missing data will not be imputed unless specified otherwise.

Partial/missing start and end dates for AEs and concomitant medications will be imputed as follows:

Partial/missing start date:

- Dates with missing day only will be imputed as the 1st of the month unless the month and year are same as the month and year of the implant date for the corresponding eye for ocular AEs or the first implant date for the non-ocular AEs in which case missing day will be imputed as the implant day for the corresponding eye for ocular AEs or the first implant day for the non-ocular AEs.
- Dates with both day and month missing will be imputed as 1 Jan unless the year is same as the year of the implant date for the corresponding eye for ocular AEs or the first implant date for the non-ocular AEs, in which case missing day and month will be imputed as the implant day and month for the corresponding eye for ocular AEs or the first implant day and month for the non-ocular AEs.
- Completely missing dates will be imputed as the implant date for the corresponding eye for ocular AEs or the first implant date for the non-ocular AEs unless the end date is on or before the implant date for the corresponding eye for ocular AEs or the first implant date for the non-ocular AEs, in which case missing date will be imputed as 1 Jan of the same year as the end date.

Partial/missing end date for AEs reported as “Resolved:”

- Dates with missing day only will be imputed as the last day of the month.
- Dates with both day and month missing will be imputed as 31 Dec.
- Completely missing end dates will have an imputed end date of 31 Dec 2023
- If the imputed date is after the date of death, then the end date will be set equal to the date of death.

The original dates will be displayed in data listings and the imputed dates will be used in derivations only (study day, treatment-emergence status, etc.).

COVID-19-related missing data or visits will not be imputed for summaries and analyses but will be reported as protocol deviations and recorded in protocol deviation log.

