13.4.3 Photopic Binocular DCIVA

Phase I/Pilot subjects will be excluded from the analysis of this endpoint.

Photopic binocular DCIVA (logMAR) at 66 cm at Post-Operative Visit 4 (Day 120 to 180 after second eye IOL implantation) will be analyzed using an ANCOVA with DCIVA as the dependent variable and treatment and site as fixed factors. The treatment effect (LS mean for Test group IOL minus LS mean for Control group IOL) will be estimated in addition to a two-sided 90% CI. The analysis will be based on observed data for ITT, mITT, and PP sets. Multiple imputation of missing data will not be applied.

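### SAP 13.4.1 and 13.4.3 attach a 90% CI to binocular DCNVA and DCIVA, which are tested for superiority at two-sided 0.05, and their no-imputation rule contradicts SAP 9.2

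*SAP*

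**What the plan says.** **Test level and success rule.** SAP 6.5 powers the four binocular secondary tests at two-sided 0.05 and orders them DCNVA, UCNVA, DCIVA, UCIVA. Protocol 13.2 rejects at p ≤ 0.05 unless otherwise specified. SAP 3.3.6 defines success as rejection of equal means with the Test mean lower, conditional on success at the preceding step.

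**Inherited method.** Protocol 13.5.4 says these endpoints are "compared between treatments using the methods described above for DCNVA and DCIVA". In Protocol 13.5.3.2 the treatment effect "will be summarized using continuous summary statistics and a two-sided 95% confidence interval". SAP 13.3.2 also uses 95% for the monocular superiority test.

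**Endpoint sections.** SAP 13.4.1 fits an ANCOVA with treatment and site; the treatment effect "will be estimated in addition to a two-sided 90% CI. The analysis will be based on observed data for ITT, mITT, and PP sets". SAP 13.4.3 does the same for DCIVA. Both end with "Multiple imputation of missing data will not be applied".

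**General missing-data rules.** SAP 9.2, which covers primary and secondary effectiveness endpoints, says missing data "will be imputed using multiple imputation Markov Chain Monte Carlo (MCMC) methods for the superiority analyses". Protocol 13.6.1 says "Unless otherwise specified in the SAP, missing data will not be imputed".

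**Analysis sets.** Protocol 13.5: "All effectiveness analyses will be presented for the ITT Set in addition to the analysis Set(s) mentioned below". Protocol 13.5.3.2 tests the mITT Phase II and III subjects and adds that "superiority will not be evaluated with the PP Set and statistical success will not depend" on the PP result.

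**Declared changes.** SAP 16 lists three changes from the protocol, all to safety analysis populations.

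**The concern.** A 90% interval belongs with a one-sided 0.05 non-inferiority bound, which is how SAP 13.3.1 uses it for BCDVA. Beside a two-sided 0.05 superiority test, a reader sees an interval that can exclude zero while the test does not reject. SAP 13.4.1 and 13.4.3 share the BCDVA section's ANCOVA, least-squares-mean and 90% wording and its lack of imputation, which suggests text carried over.

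The missing-data rules cannot both be followed. 9.2 names secondary endpoints and makes no exception; 13.4.1 and 13.4.3 forbid what it requires. The two sections also list ITT, mITT and PP without saying which decides. Binocular DCNVA is the gate to the other three tests, and the case in SAP 9.4 for making no multiplicity adjustment assumes one pre-specified analysis at each step.

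**Working it through.** **Inputs (SAP 6.5).** 276 Test and 138 Control evaluable; difference −0.10 logMAR; SD 0.20 (binocular DCNVA) and 0.15 (binocular DCIVA); two-sided 0.05.

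**Plan's own figure.** SE = SD × √(1/276 + 1/138) = SD × 0.10426, which is 0.02085 at SD 0.20 and 0.01564 at SD 0.15. With 412 degrees of freedom and the noncentral t, power is 99.76% and above 99.9%. The stated 99% is reproduced for both.

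**Half-widths.** t(0.95) = 1.6486 and t(0.975) = 1.9657; ratio 1.6486/1.9657 = 0.839, so the 90% interval is 16% narrower.

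| Endpoint | SE | 90% half-width | 95% half-width |
|---|---|---|---|
| DCNVA, SD 0.20 | 0.02085 | 0.0344 | 0.0410 |
| DCIVA, SD 0.15 | 0.01564 | 0.0258 | 0.0307 |

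Fitting 20 to 25 sites changes these by less than 0.0001. An observed difference between the two half-widths excludes zero at 90% but gives p > 0.05.

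**How often that would happen.** P(90% interval excludes zero) minus P(95% interval excludes zero), in the favourable direction:

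- True difference −0.10: DCNVA 0.99916 − 0.99763 = 0.0015; DCIVA 0.000004.
- The gap is widest when the true difference is about (1.6486 + 1.9657)/2 = 1.807 SE. That is 1.807 × 0.02085 = 0.038 for DCNVA and 1.807 × 0.01564 = 0.028 for DCIVA. There it reaches 12.6%.

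**Can the 13.3.2 imputation model be run?** Its code imputes Visit 4 from the Visit 3A value within treatment arm. SAP Table 1 makes Visit 3A a first-eye visit. In the protocol's Appendix A flow chart the photopic binocular rows carry these marks:

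| Row | Marks | Visits they fit |
|---|---|---|
| UCNVA | 3 | 3B, 4, 5 |
| UCIVA | 3 | 3B, 4, 5 |
| DCNVA | 2 | 4, 5 |
| DCIVA | 2 | 4, 5 |

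Some columns moved when the table was extracted, so this relies on mark counts, which do not change with a column shift. The counts indicate no binocular DCNVA or DCIVA value before Visit 4, so the code has no predictor for these endpoints. The SAP's split follows the same line: observed data under the DCNVA and DCIVA headings, imputation seeds under the UCNVA and UCIVA headings.

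**Steps 2 and 4.** The text of 13.4.2 and 13.4.4 names binocular DCNVA and DCIVA under the UCNVA and UCIVA headings. Read literally, DCNVA and DCIVA are told both to impute and not to impute, and UCNVA and UCIVA have no analysis text. Both sections also refer to 13.3.2 and so inherit its Visit 3A predictor, a visit at which no binocular value is planned.

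**The case against.** The strongest reply is that leaving out imputation looks deliberate. With no earlier binocular value there is nothing for the 13.3.2 model to use, an endpoint-specific section normally governs a general one, and Protocol 13.6.1 makes no imputation the default. This stands: 9.2 is the over-general sentence, and the remedy need not restore imputation.

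It also limits a stronger reading, that the SAP silently dropped a protocol-mandated imputation. The protocol points both ways: 13.5.4 imports the monocular method, which imputes, while 13.6.1 defaults to none. The omission from SAP 16 is therefore firm only for the interval level. The conflict between 9.2 and the endpoint sections lies within the SAP and remains.

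The second reply is that the 90% interval decides nothing. This is also correct. A reader might infer that the gatekeeping test is really run at two-sided 0.10 and that the error rate of the sequence is inflated. The documents do not support that, because no sentence makes the interval the criterion and the SAP 3.3.6 rule stands.

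The third reply is that the ranking of analysis sets can be recovered from the protocol (mITT tested, ITT in addition, PP not evaluated for superiority). It can, but 13.4.1 and 13.4.3 list all three on an equal footing, and one clause would settle it.

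**Conclusion.** The point holds in two limited parts.

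1. **Interval level.** The 90% interval in 13.4.1 and 13.4.3 does not match the two-sided 0.05 test or the inherited 95% method. It is 16% narrower. At the planned effect the two intervals would disagree about zero in 0.15% of trials for DCNVA and fewer than 0.001% for DCIVA; the 12.6% peak needs a true effect roughly a third of the planned one. A changed conclusion is unlikely.
2. **Missing data.** The SAP gives incompatible instructions for steps 1 and 3, and the only imputation model it specifies cannot be run for those endpoints as written. The documents do not allow the effect on the estimates to be sized.

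The primary conclusions are not affected. The figures rest on the planned SDs and 276/138 evaluable subjects; the point about earlier visits rests on flow-chart mark counts and should be confirmed against the original table. It should be fixed because it concerns the gatekeeping step and the correction is small.

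**What to change.** 1. In SAP 13.4.1 and 13.4.3 change 90% to 95%. State that the test is two-sided at p ≤ 0.05, that the mITT Set restricted to Phase II and III is decisive, and that ITT and PP are supportive.
2. Amend SAP 9.2 to except binocular DCNVA and DCIVA, with observed data as primary, and record this in section 16 for transparency. If imputation is wanted instead, specify a model with an auxiliary variable that exists, such as earlier monocular values of the same measure.
3. In SAP 13.4.2 and 13.4.4 correct the endpoint names in the text to UCNVA and UCIVA. Replace the inherited Visit 3A predictor with an earlier binocular visit that has data; the mark counts point to Visit 3B, to be confirmed on the original flow chart.

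The cost is SAP wording, plus one specified imputation model per endpoint if the alternative in item 2 is chosen. No subjects are added, since power at two-sided 0.05 is already 99.8% for DCNVA and above 99.9% for DCIVA.

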13.4.2 Photopic Binocular UCNVA

Phase I/Pilot subjects will be excluded from the analysis of this endpoint.

Photopic binocular DCNVA (logMAR) at 40 cm at Post-Operative Visit 4 (Day 120 to 180 after second eye IOL implantation) will be analyzed similarly to the analyses of the second primary effectiveness endpoints described in [Section 13.3.2](#) using a seed of 178029470 for imputation of missing data.

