## 8.0 TRIAL FRAME ASTIGMATISM SIMULATION

Participating subjects should have the following characteristics (in both eyes) upon having consented to the Trial Frame Astigmatism Simulation sub-study:

1. Signed consent (no later than Visit 5) to participate in the sub-study
2. Completed visit 5
3. Have a best-corrected distance visual acuity of 20/25 or better as noted in each eye at Visit 5
4. Subjects should not have corneal edema, increased IOP or any AE / SAE at Visit 5, as per the reportable AEs/ SAEs clarified in section 12.4.1 of the protocol.
5. In addition, subjects must be willing to complete their participation on the Trial Frame sub-study between 2 and 30 days after completion of Visit 5.
6. Subjects with oblique post-operative residual astigmatism (axis between 30 to 60 degrees or 120 to 150 degrees) will be excluded from participation in the sub-study.

Enrollment will be sequential with consecutive subjects enrolled onto the Trial Frame astigmatism simulation sub-study at each site in order of their completion of post-operative Visit 5 and based on their eligibility. The subject will provide consent for the Trial Frame astigmatism simulation sub-study by completion of Visit 5 and return at Visit 6 to undergo the trial frame evaluation to assess distance-corrected visual acuities with various amounts of astigmatism. Eligibility for the sub-study will be confirmed by the completion of Visit 5 and

subjects will be enrolled in it when the Informed Consent document is signed. Visit 6 will include review/update of concomitant medications, adverse events, and measurement of monocular distance corrected visual acuity for far (4 m), intermediate (66 cm), and near (40 cm) distance under photopic conditions with varying degrees of simulated residual astigmatism with 2.00 D, 1.5 D, and 1.0 D CYL. Participants in the sub-study will be seen at only one visit (Visit 6) for the trial frame evaluation which will complete their participation in the study. Assessments are shown in the Study Flow Chart in [Appendix A](#).

The below assessments will be recorded:

- i. For the (4-meter) manifest-corrected distance (4 m) testing:
  - Visual acuity will be assessed without astigmatic blur; and
  - With astigmatic blur for each astigmatic condition (power/axis orientation);
- ii. For the distance corrected intermediate (66 cm) testing :
  - Visual acuity will be assessed without astigmatic blur; and

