6.1 Phase I/Pilot

A sample size of 24 DCNVA measurements at each of three distances will yield a probability of at least 98% of selecting the best distance when the difference (in logMAR units) between the best distance and the second-best distance is at least 0.1 and the data are normally distributed with a standard deviation (SD) of 0.15. The first 27 Test group subjects will be

enrolled in Phase I/Pilot to allow for at least 24 Test group subjects at Post-Operative Visit 3A (Day 30 to 60 after first eye IOL implantation).

A sample size of 24 DCIVA measurements at each of three distances will yield a probability of at least 98% of selecting the best distance when the difference (in logMAR units) between the best distance and the second-best distance is at least 0.1 and the data are normally distributed with a SD of 0.15. The first 27 Test group subjects will be enrolled in Phase I/Pilot to allow for at least 24 Test group subjects at Post-Operative Visit 3A (Day 30 to 60 after first eye IOL implantation).

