6.5 Secondary Effectiveness Endpoints

Secondary effectiveness endpoint hypotheses will be tested hierarchically in the order: DCNVA, UCNVA, DCIVA, and UCIVA. Approximately the first 24 evaluable Test group (Group 1) subjects and 12 evaluable Control group (Group 2) subjects will be excluded from the near and intermediate visual acuity hypothesis tests, leaving an expected evaluable sample size of approximately 276 Test group subjects and 138 Control group subjects to be included in the near and intermediate VA hypothesis tests.

Regarding photopic binocular distance-corrected near visual acuity (DCNVA) at 40 cm at Post-Operative Visit 4 (Day 120 to 180 after second eye IOL implantation), a two-group t-test with a 0.05 two-sided significance level will have 99% power to detect a difference in means of -0.10 logMAR units, assuming that the common SD is 0.200 units, when the sample sizes in the two groups are 276 and 138 subjects, respectively (a total sample size of 414 subjects).

Regarding photopic binocular uncorrected near visual acuity (UCNVA) at 40 cm at Post-Operative Visit 4 (Day 120 to 180 after second eye IOL implantation), a two group t-test with a 0.05 two-sided significance level will have 99% power to detect a difference in means of -

0.10 logMAR units, assuming that the common SD is 0.20 units, when the sample sizes in the two groups are 276 and 138 subjects, respectively (a total sample size of 414 subjects).

Regarding photopic binocular distance-corrected intermediate visual acuity (DCIVA) at 66 cm at Post-Operative Visit 4 (Day 120 to 180 after second eye IOL implantation), a two group t-test with a 0.05 two-sided significance level will have 99% power to detect a difference in means of -0.10 logMAR units, assuming that the common SD is 0.15 units, when the sample sizes in the two groups are 276 and 138 subjects, respectively (a total sample size of 414 subjects).

Regarding photopic binocular uncorrected intermediate visual acuity (UCIVA) at 66 cm at Post-Operative Visit 4 (Day 120 to 180 after second eye IOL implantation), a two group t-test with a 0.05 two-sided significance level will have 99% power to detect a difference in means of -0.10 logMAR units, assuming that the common SD is 0.20 units, when the sample sizes in the two groups are 276 and 138 subjects, respectively (a total sample size of 414 subjects).

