13.3.2 Photopic Monocular DCNVA

Phase I/Pilot subjects will be excluded from the analysis of this endpoint.

Photopic monocular DCNVA (logMAR) at 40 cm in first eyes at Post-Operative Visit 4 (Day 120 to 180 after second eye IOL implantation) will be summarized using continuous summary statistics in logMAR units by treatment assignment for the mITT Set.

If there are missing mITT Set monocular DCNVA data in first eyes at Post-Operative Visit 4 (Day 120 to 180 after second eye IOL implantation), then missing data will be imputed using the MCMC multiple imputation method. A total of 30 imputation datasets will be created. After imputation of missing data, the statistical hypotheses will be tested using an ANCOVA model with treatment and site as fixed factors by imputation.

SAS® code for the MCMC multiple imputation:

```
PROC MI DATA=indata OUT=mcmc NIMPUTE=30 SEED= 1091148178;  
  BY trt;  
  MCMC INITIAL=EM;  
  VAR V3 V4;  
  RUN;
```

where

- trt = treatment
- v3 = actual value at Visit 3A
- v4 = actual value at Post-Operative Visit 4 (Day 120 to 180 after second eye IOL implantation)

An overall p-value resulting from the multiple imputation method will be estimated. The treatment effect (LS mean for Test group IOL VA minus LS mean Control group IOL VA) in logMAR units and a two-sided 95% CI will be provided. If the p-value from the multiple imputation analysis is less than or equal to 0.05 and the treatment effect is less than or equal to -0.10 (i.e., the Test lens mean logMAR VA is at least 0.10 less than the mean for the control), then it will be concluded that the Test IOL is statistically and clinically successful (i.e., superior to the Control IOL) in this outcome.

The previous continuous summary statistics will also be provided for the PP Set. However, superiority will not be evaluated with the PP Set, and statistical success will not depend upon the results of the PP analysis.

As a sensitivity analysis, observed DCNVA (logMAR) at 40 cm in first eyes at Post-Operative Visit 4 (Day 120 to 180 after second eye IOL implantation) will be compared between treatment groups using an ANCOVA model with treatment and site as fixed factors. The treatment effect (LS mean for Test group IOL VA minus LS mean Control group IOL VA) in logMAR units and a two-sided 95% CI will be provided. The analysis will be for the ITT set.

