13.4.4 Photopic Binocular UCIVA

Phase I/Pilot subjects will be excluded from the analysis of this endpoint.

Photopic binocular DCIVA (logMAR) at 66 cm at Post-Operative Visit 4 (Day 120 to 180 after second eye IOL implantation) will be analyzed similarly to the analyses of the second primary effectiveness endpoints described in [Section 13.3.2](#) using a seed of 1303271003 for imputation of missing data.

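### SAP 13.4.1 to 13.4.4, binocular secondary endpoints: two sections name the wrong acuity measure and inherit a predictor not collected binocularly; the other two contradict SAP 9.2 on imputation and give 90% intervals for two-sided 0.05 tests

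*SAP*

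**What the plan says.** SAP 3.2.4, 3.3.6 and 6.5 define four binocular secondary effectiveness endpoints at Visit 4. SAP 6.5 fixes their order: "Secondary effectiveness endpoint hypotheses will be tested hierarchically in the order: DCNVA, UCNVA, DCIVA, and UCIVA". Each is a superiority test at two-sided 0.05.

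The operative text is in SAP 13.4:

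- **13.4.1 (DCNVA) and 13.4.3 (DCIVA):** a model with treatment and site, fitted to observed data, with a two-sided 90% interval. On missing data, 13.4.1 says "Multiple imputation of missing data will not be applied", and 13.4.3 says the same.
- **13.4.2 (heading UCNVA):** "Photopic binocular DCNVA (logMAR) at 40 cm at Post-Operative Visit 4 (Day 120 to 180 after second eye IOL implantation) will be analyzed similarly" to 13.3.2, with its own seed.
- **13.4.4 (heading UCIVA):** "Photopic binocular DCIVA (logMAR) at 66 cm at Post-Operative Visit 4 (Day 120 to 180 after second eye IOL implantation) will be analyzed similarly" to 13.3.2, with its own seed.

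The imputation code in 13.3.2 runs by arm on two variables, the Visit 4 value and V3, defined as "v3 = actual value at Visit 3A". SAP 6.1 dates that visit from first-eye surgery: "Post-Operative Visit 3A (Day 30 to 60 after first eye IOL implantation".

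For primary and secondary effectiveness endpoints, SAP 9.2 says that missing data "will be imputed using multiple imputation Markov Chain Monte Carlo (MCMC) methods for the superiority analyses". Protocol 13.5.4 carries the monocular DCNVA and DCIVA methods over to all four binocular endpoints; those methods include imputation and a 95% interval. Protocol 13.6.1 makes no imputation the default unless the SAP specifies it.

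**The concern.** SAP 13.4 is the text that a programmer would follow. Read literally, binocular DCNVA and DCIVA each receive two conflicting analyses (observed data in one section, imputed in the next), and UCNVA and UCIVA receive none. The imputation borrowed for UCNVA and UCIVA rests on a visit at which the binocular measure is not taken. For DCNVA and DCIVA the general rule and the endpoint rule give opposite instructions on missing data. Binocular DCNVA and UCNVA are the first two steps of the fixed sequence, so unclear rules there come before every later claim. What is at stake is pre-specification: the imputation model and missing-data rule should not be open to choice once results can be seen.

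**Working it through.** **1. Which variable.** In 13.4.2 and 13.4.4 the heading and the sentence disagree. SAP 3.2.4, 3.3.6 and 6.5 and Protocol 13.5.4 all list UCNVA second and UCIVA fourth. The headings are right and the sentences are wrong.

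**2. Which predictor.** Protocol Appendix A has no binocular near or intermediate acuity at Visit 3A. Monocular first-eye UCNVA and UCIVA are scheduled there, but the SAP does not say to use them. Binocular UCNVA is marked at Visits 3B, 4 and 5. In the flow-chart text available here, binocular UCIVA is marked under Visits 4, 5 and 6. Protocol Appendix B 8.0 limits Visit 6 acuity to "measurement of monocular distance corrected visual acuity for far (4 m), intermediate (66 cm), and near (40 cm) distance under photopic conditions", so that row looks shifted by one column and probably means 3B, 4 and 5. Binocular DCNVA and DCIVA appear to be scheduled only at Visits 4 and 5.

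**3. Which missing-data rule.** SAP 9.2 covers secondary superiority analyses, and its allowance for exceptions extends only to safety and exploratory endpoints. SAP 13.4.1 and 13.4.3 nevertheless exclude imputation.

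**4. The plan's own power.** Inputs from SAP 6.5: n = 276 and 138, difference -0.10, SD 0.20 (0.15 for DCIVA), two-sided 0.05.

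- SE = SD × √(1/276 + 1/138) = SD × 0.10426, which is 0.02085 at SD 0.20 and 0.01564 at SD 0.15.
- Power at SD 0.20 = Φ(0.10/0.02085 - 1.96) = Φ(2.84) = 99.8% (noncentral t with 412 df: 99.76%).
- Power at SD 0.15 is above 99.99%.

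The stated 99% is reproduced.

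**5. Effect of the missing-data choice.** Planned Phase II and III subjects: 334 - 27 = 307 Test and 167 - 14 = 153 Control, 460 in all. The documents give no missing rate for Visit 4 (10% is the allowance for losses over the whole follow-up), so I assume a fraction f of 2% to 15%, missing completely at random. The complete-case SE is 0.20 × √[1/(307(1 - f)) + 1/(153(1 - f))]. An imputation predictor with correlation ρ multiplies the variance by (1 - ρ²f). I assume ρ from 0.4 to 0.8.

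| Missing | Complete-case SE | Power | SE ratio, ρ 0.4 | SE ratio, ρ 0.8 | Power, ρ 0.8 |
|---|---|---|---|---|---|
| 2% (9) | 0.01999 | 0.9988 | 0.998 | 0.994 | 0.9989 |
| 5% (23) | 0.02031 | 0.9984 | 0.996 | 0.984 | 0.9988 |
| 10% (46) | 0.02086 | 0.9976 | 0.992 | 0.968 | 0.9986 |
| 15% (69) | 0.02147 | 0.9964 | 0.988 | 0.951 | 0.9983 |

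The largest gain is 0.9983 - 0.9964 = 0.0019, about 0.2 points. At SD 0.15 power exceeds 0.9999 throughout.

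A simulation (800 runs, 10% missing, imputation by arm, 30 imputations, ρ 0.8) gave mean SEs of 0.0202 with the predictor, 0.0209 for imputation without one, and 0.0208 for complete cases. Imputation without a usable predictor therefore adds nothing.

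**6. Interval width** at 276 and 138 (t multipliers 1.649 and 1.966 on 412 df):

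- SD 0.20: half-width 0.0344 at 90%, 0.0410 at 95%.
- SD 0.15: half-width 0.0258 at 90%, 0.0307 at 95%.

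The ratio is 0.839, so the 90% interval is 16% narrower. The success rules in SAP 3.3.6 and 13.3.2 use the p-value and the direction or size of the estimate, not a confidence limit.

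**The case against.** The case for leaving the text alone has several parts, and much of it stands.

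- **The labels are clerical.** The headings and endpoint lists settle the meaning. A reader might infer that UCNVA and UCIVA go unanalysed, or that the fixed sequence is blocked. The documents do not support that, because the intent is recoverable from every other section.
- **The protocol does not clearly require imputation here.** A reader might infer that 13.4.1 and 13.4.3 depart from the protocol and that SAP section 16 fails to list the change. Protocol 13.5.4 does not mention imputation itself, and 13.6.1 makes no imputation the default unless the SAP says otherwise. The protocol is ambiguous, so an unlisted departure is not established. That does not resolve the matter, because 13.6.1 defers to the SAP and the SAP contradicts itself.
- **A missing-data rule is stated.** Sections 13.4.1 and 13.4.3 say observed data only, so it would be wrong to say that the programmer has no rule. The defect is that 9.2 says the opposite without making an exception.
- **The predictor is defined.** It is the Visit 3A value, and a predictor need not be binocular. What fails is narrower: the same binocular measure is not collected at Visit 3A, and no substitute is named.
- **Dropping imputation may be deliberate.** Binocular DCNVA and DCIVA seem to have no binocular value before Visit 4. The SAP does not give this as the reason.
- **Little turns on it numerically.** This is correct.

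**Conclusion.** The four analysis sections are wrong or contradictory as written, and the effect is small. The wrong labels, the Visit 3A predictor, the clash between 9.2 and 13.4.1/13.4.3, and the mismatch between 90% intervals and two-sided 0.05 tests all follow from the printed text. Under the assumptions shown, power at -0.10 logMAR stays above 99.6%, and imputation with a usable predictor moves it by at most about 0.2 points. The 90% interval is a reporting mismatch. A reader might take it as a looser success criterion, but no secondary success rule refers to it. The primary endpoints and overall trial success are unaffected.

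The figures rest on missing rates of 2% to 15%, correlations of 0.4 to 0.8 and data missing completely at random, none of which the documents state. They describe precision only; they say nothing about bias if missing values are related to outcome. The reading of the binocular UCIVA schedule is less certain than the rest, because it depends on a flow-chart row that looks shifted. The point is worth correcting because these are pre-specified, hierarchically tested endpoints and the correction is cheap.

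**What to change.** Before unmasking:

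1. In SAP 13.4.2 name UCNVA, and in 13.4.4 name UCIVA. Keep the printed seeds.
2. For these two, state one collected imputation predictor. Either the binocular Visit 3B value of the same measure (checked for UCIVA against the original flow chart) or the monocular first-eye Visit 3A value would serve. The choice matters less than writing it down.
3. Make SAP 9.2 agree with 13.4.1 and 13.4.3. Either except binocular DCNVA and DCIVA in 9.2, or restore imputation for them with a collected predictor such as the monocular first-eye Visit 3A value already used in 13.3.2 and 13.3.3.
4. Report two-sided 95% intervals in 13.4.1 and 13.4.3, to match the tests and the protocol method that 13.5.4 carries over.

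Listing the observed-data rule in SAP section 16 is optional, for transparency.

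The cost is a few lines of SAP text. No new data are needed: monocular first-eye values are scheduled at Visit 3A for all four measures, and binocular UCNVA is scheduled at Visit 3B. Only the choice of Visit 3B for UCIVA depends on the flow-chart check.
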